Note: For all patients, as part of the physical examination, a thorough head and neck evaluation to monitor for non-cuSCC, consisting of at least a visual inspection of the oral mucosa and lymph node palpation, must be performed by the site investigator every 13 ± 2 weeks during the study drug treatment period. Once a patient completes the treatment period or discontinues study drug early, a thorough evaluation of the head and neck by the study investigator will be performed at the end-of-treatment visit as part of the physical examination. Once a patient completes the treatment period or discontinues study drug early, a thorough head and neck evaluation to monitor for non-cuSCC will occur (as part of the physical examination for patients who continue to have physical examinations) at 13 ± 2 weeks and 26 ± 2 weeks from the last dose of study drug. For patients who no longer require physical examinations, the head and neck examination will occur independently at 13 ± 2 weeks and 26 ± 2 weeks from the last dose of study drug (except in the case of withdrawal of consent or loss to follow-up).

Patients with signs or symptoms consistent with head and neck cancer as determined by the site investigator will have a complete evaluation of the head and neck by a head and neck surgeon/otorhinolaryngologist or his or her designee who is experienced in the diagnosis and management of SCC of the head and neck: every 26 ± 2 weeks during the study drug administration period. Once a patient completes the treatment period or discontinues study drug early, a complete evaluation of the head and neck by a head and neck surgeon/otorhinolaryngologist will be performed at 26 ± 2 weeks after the last dose of study drug (except in the case of withdrawal of consent or loss to follow-up).

- All patients will have a colonoscopy to the cecum, with adequate bowel preparation, by a gastroenterologist or his or her designee who is experienced in the colonoscopic diagnosis of colorectal polyps and colorectal cancer within 3 months of discontinuation of study drug. All polyps found at any of the colonoscopies will need to be adequately resected.
- Hematology: Day 1 (± 3 days) of each cycle and the end-of-treatment visit
- Serum chemistry and liver function tests: Cycle 1 (Days 8, 15, and 22, each ± 3 days), Cycle 2 (Days 1 and 15, each ± 3 days), Day 1 (± 3 days) of every subsequent 4-week cycle and at the end-of-treatment visit

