5.1.2.3.4 Colorectal Polyps

For select patients with known personal history of adenomatous colorectal polyps or colorectal cancer, family history of colon cancer in which a first- and/or second-degree relative has been diagnosed with colorectal cancer at or after the age of 60 years, or signs or symptoms that could be related to colon cancer as determined by the site investigator or designee, a screening colonoscopy will be conducted. Patients with family history of inherited colon cancer syndromes and/or history of colon cancer in which a first- and/or second-degree relative has been diagnosed with colorectal cancer before the age of 60 years will be excluded from this study.

Colonoscopy must be complete to the cecum, with adequate bowel preparation, and must be performed within the 90-day screening period by a gastroenterologist or his or her designee who is experienced in the colonoscopic diagnosis of colorectal polyps and colorectal cancer. All visualized polyps found at the screening or subsequent colonoscopies will need to be adequately resected. For select patients (described above), the screening colonoscopy is not required if colonoscopy to the cecum with adequate bowel preparation and adequate resection of all visualized polyps was performed within 1 year of the start of the 90-day screening period, unless the site investigator deems it necessary. Please note that patients with a personal history of more than three (>3) adenomatous colorectal polyps or a personal history of adenomatous colorectal polyp(s) >2 cm in size will be excluded from this study; this also applies to the screening colonoscopy for the select patients described above (see also Section 4.1.2).

All patients will be required to undergo a post-treatment colonoscopy within 3 months of discontinuation of study drug.

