5.2.3 Non-Serious Adverse Events of Special Interest (Immediately Reportable to Roche)

Non-serious adverse event of special interest are required to be reported by the investigator to the Sponsor within 24 hours after learning of the event (see Section 5.4.2 for reporting instructions). Adverse events of special interest for this study include the following:

- Grade ≥ 3 photosensitivity
- Grade 4 elevations of AST, ALT, serum bilirubin OR cases of elevated ALT or AST in combination with either an elevated bilirubin or clinical jaundice, as defined in Section 5.3.5.6
- cuSCC (including KA)
- Grade ≥ 3 QT interval prolongation
- Gastrointestinal polyps
- Suspected transmission of an infectious agent by study drug

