5.3.1 Adverse Event Reporting Period

Investigators will seek information on adverse events at each patient contact. All adverse events, whether reported by the patient or noted by study personnel, will be recorded in the patient's medical record and on the Adverse Event eCRF.

After informed consent has been obtained **but prior to initiation of study drug**, only serious adverse events caused by a protocol-mandated intervention should be reported (e.g., serious adverse events related to invasive procedures such as biopsies).

After initiation of study drug, all adverse events, regardless of relationship to study drug, will be reported up to and including 28 days after the last dose of study drug. After

this period, investigators should report any deaths, serious adverse events, or other adverse events of concern that are believed to be related to prior treatment with study drug (see Section 5.6). In addition, all new primary malignancies will be reported *until end of study* (see Section 3.2), whether or not a patient has exhibited recurrence of melanoma while in the study.

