5.4 IMMEDIATE REPORTING REQUIREMENTS FROM INVESTIGATOR TO SPONSOR

The investigator must report the following events to the Sponsor within 24 hours after learning of the event, regardless of relationship to study drug:

- Serious adverse events
- Non-serious adverse event of special interest
- Pregnancies

The investigator must report new significant follow-up information for these events to the Sponsor within 24 hours after becoming aware of the information. New significant information includes the following:

- New signs or symptoms or a change in the diagnosis
- Significant new diagnostic test results
- Change in causality based on new information
- Change in the event's outcome, including recovery
- Additional narrative information on the clinical course of the event

Investigators must also comply with local requirements for reporting serious adverse events to the local health authority and IRB/EC.

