Appendix 1 Schedule of Assessments (cont.)

prior to the start of the 90-day screening period and found to be normal, need not be repeated at screening.

- ^p For patients with personal history of adenomatous colon polyps or colorectal cancer, family history of colon cancer in which a first- and/or second-degree relative has been diagnosed with colorectal cancer at or after the age of 60 years, or signs or symptoms that could be related to colon cancer as determined by the site investigator or designee, colonoscopy to the cecum, with adequate bowel preparation, will be performed by a gastroenterologist or his or her designee who is experienced in the colonoscopic diagnosis of colorectal polyps and colorectal cancer (within the 90-day screening period). For select patients (described above), the screening colonoscopy is not required if colonoscopy to the cecum with adequate bowel preparation and adequate resection of all visualized polyps was performed within 1 year of the start of the 90-day screening period, unless the site investigator deems it necessary. All patients must have colonoscopy within 3 months of discontinuation of study drug. All polyps found at the screening or subsequent colonoscopies will need to be adequately resected. Please note that a patient with a personal history of more than three (> 3) adenomatous colorectal polyps or a personal history of adenomatous colorectal polyp(s) > 2 cm in size will be excluded from this study; this also applies to the screening colonoscopy for the select patients described above (see Section 4.1.2).
- ^q Stool sample will be collected at screening, Cycle 6, Day 1 (± 2 weeks), and at the end-of-treatment visit (± 2 weeks). If the stool occult sample is positive at screening, the patient must be cleared for study inclusion by a gastroenterologist or appropriately trained designee.
- ^r Includes hemoglobin, hematocrit, platelet count, WBC count, WBC differential (ANC), lymphocyte, monocyte, eosinophil, and basophil counts, and other cell counts.
- ^s Includes sodium, potassium, chloride, bicarbonate, glucose, BUN or urea, creatinine, calcium, total bilirubin, albumin, ALT, AST, alkaline phosphatase, phosphorus, magnesium, LDH, and uric acid.
- ^t If a patient discontinues study drug early, a serum pregnancy test will be performed at 12 ± 2 weeks and 26 ± 2 weeks after the last dose of study drug (except in the case of withdrawal of consent or loss to follow-up).

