- ^{ff} After initiation of study drug, all adverse events regardless of relationship to study drug will be reported up to and including 28 days after the last dose of study drug. Thereafter, only SAEs, any death, and other adverse events of concern that are believed to be related to prior treatment with study drug should be reported.
- ^{gg} After informed consent has been obtained but prior to initiation of study drug, only SAEs caused by a protocol-mandated intervention should be reported (e.g., SAEs related to invasive procedures such as biopsies).
- ^{hh} Patient-reported outcomes will be elicited from all patients with use of the EORTC QLQ-C30 questionnaire, which should be self-administered at the investigative site prior to the completion of other study assessments and the administration of study treatment. In post-treatment follow-up, the EORTC QLQ-C30 questionnaire will be completed every 13 ± 2 weeks until recurrence or occurrence of a new primary melanoma or *until end of study* (see Section 3.2), whichever occurs first.
- ⁱⁱ Serum and plasma samples for exploratory biomarker assessments include one blood sample in a serum separator tube (6 mL) and one 6-mL blood sample that has been anti-coagulated in EDTA. Samples are collected at Cycle 1 (Day 1 pre-dose and Day 15 ± 3 days), Cycle 2 (Day 1 ± 3 days), Cycle 3 (Day 1 ± 3 days), at the end-of-treatment visit, and every 52 ± 2 weeks after last dose of study drug, at the recurrence of melanoma, occurrence of a new primary melanoma, or *until end of study*, whichever occurs earlier. In the event of melanoma recurrence or occurrence of a new primary melanoma during study treatment or if the patient discontinues study treatment because of other reasons, a sample should be taken upon drug discontinuation.

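### For gastrointestinal polyps found at the post-treatment colonoscopy after day 28, the protocol gives conflicting rules on whether reporting depends on the investigator's causality opinion

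*Protocol*

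**What the plan says.** - **Status of the event.** Protocol 5.2.3 lists "Gastrointestinal polyps" among the non-serious AESIs, with no grade threshold.
- **How polyps are found.** Protocol 5.1.2.3.4: "All patients will be required to undergo a post-treatment colonoscopy within 3 months of discontinuation of study drug". Sections 4.5.1.7 and 4.5.2.2 and Appendix 1 footnote p give the same window. At screening, only patients with certain histories or symptoms need a colonoscopy, and a recent one can stand in for it. The post-treatment colonoscopy is thus the only one required of everyone.
- **Period of all-causality reporting.** Under 5.3.1, adverse events of any cause "will be reported up to and including 28 days after the last dose of study drug".
- **Rule after that.** Section 5.3.1: "investigators should report any deaths, serious adverse events, or other adverse events of concern that are believed to be related to prior treatment". Appendix 1 footnote ff, on both the adverse event row and the SAE/AESI row: "Thereafter, only SAEs, any death, and other adverse events of concern that are believed to be related to prior treatment with study drug". Section 5.3.1 adds new primary malignancies as a further category reported to end of study; a benign polyp is not one.
- **The other rule.** Section 5.4 requires SAEs, non-serious AESIs and pregnancies within 24 hours, "regardless of relationship to study drug", with no end date. In the Appendix 1 grid, the SAE/AESI row is marked in columns after the end-of-treatment visit, where the general adverse event row is not.
- **Analysis.** Protocol 6.5 summarises AESIs by arm with a pointer to 5.2.3. SAP 4.7.2 summarises events of interest by arm; its examples do not include polyps. It refers to treatment-emergent events without defining a window.

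**The concern.** Polyps were made an AESI because adenomatous colonic polyps had been reported in patients on vemurafenib (Protocol 3.3.4.2 and 5.1.1). With no baseline colonoscopy required of most patient categories, the evidence on a drug effect comes from comparing the arms at the post-treatment examination. That comparison needs the same reporting rule in both arms and at all sites.

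If a site applies 5.3.1 and footnote ff to a polyp found after day 28, it reports the polyp only when the investigator believes it related to study drug. Protocol 3.3.3 accepts that vemurafenib's toxicity may make masking difficult, so that belief could differ by arm. A site that applies 5.4 would report every such polyp. The by-arm count would then mix two rules, one of which depends on opinion.

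**Working it through.** The plan states no figure to reproduce. The check has two parts.

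**1. How much of the colonoscopy window lies after all-causality reporting ends**

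Inputs: the window is 3 months from discontinuation (4.5.2.2, 5.1.2.3.4, footnote p), and all-causality reporting runs to day 28 after the last dose (5.3.1). Assumptions: discontinuation and last dose are the same day; 3 months is 90 to 92 days, with 84 days (12 weeks) as a low bound.

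Share after day 28 = (W − 28) / W

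| W (days) | Days after day 28 | Share |
|---|---|---|
| 84 | 56 | 66.7% |
| 90 | 62 | 68.9% |
| 92 | 64 | 69.6% |

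This is a share of calendar days, not of patients. The documents do not say when colonoscopies were done. In the extracted Appendix 1 grid, which is broken, the mark appears to sit at the end-of-treatment visit (28 ± 3 days, so days 25 to 31), but footnote p allows the full 3 months.

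**2. Which rule applies to a non-serious polyp found after day 28**

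- *Section 5.3.1.* The relatedness phrase may qualify all three items in the sentence or only the last. A non-serious polyp is neither a death nor an SAE, so if the sentence covers it at all, it falls in the last item and is filtered on either reading.
- *Footnote ff.* It is restrictive and is attached to the AESI row. If a polyp counts as an event of concern, it is filtered by relatedness. If it does not, the footnote taken literally leaves it out altogether, which contradicts the follow-up marks in the same row.
- *Section 5.4.* It names AESIs, excludes causality as a condition and gives no end date. Read alone, it requires the polyp to be reported.
- *Comparison with other events.* Section 5.1.2.3.3 says that cutaneous squamous cell carcinoma is reported whether it arises on or after treatment and whatever its relationship to drug. Section 5.1.2.3.5 does the same for other new malignancies. Section 5.1.2.3.4, on polyps, has no reporting sentence.

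The text therefore supports two answers and does not rank them.

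**Effect on the comparison.** Let *p* be the true proportion with a polyp, equal in both arms. Let *s* be the share of polyps found after day 28 at sites that apply the filter, and *r* the probability that the investigator calls such a polyp related. Reported incidence is *p*[(1 − *s*) + *s r*]. The ratio of arms is [(1 − *s*) + *s r*(vemurafenib)] / [(1 − *s*) + *s r*(placebo)]. It equals 1 only if *s* = 0 or the two *r* values agree. The documents give neither *s* nor *r*, so the bias cannot be sized.

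**The case against.** A reader might infer that after day 28 the protocol reports only polyps judged drug-related. The documents do not support that.

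- Section 5.4 and the 24-hour duty in 5.2.3 cover AESIs with no end date, and the opening of 5.3 says that reporting follows 5.3 together with 5.4 through 5.6. The AESI row in Appendix 1 outlasts the general adverse event row, which suggests that AESI collection was meant to continue.
- The relatedness phrase in 5.3.1 may attach only to its last item. Section 5.3.5.7 supports this: deaths not due solely to melanoma recurrence are reported whatever their relationship to drug, although 5.3.1 lists deaths in the same sentence. Section 5.6, to which 5.3.1 refers, does filter every item, but for patients who have left the study. A patient attending the colonoscopy is normally still in follow-up.
- Section 4.4.1 asks sites to record procedures in the study period with their clinical findings, without a causality test. Findings may exist even where no AESI was reported.
- Protocol 6.5 already brings polyps into the by-arm AESI summary through 5.2.3, and the SAP's list is only of examples.

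These points stand against a claim that late unrelated polyps were excluded by design or lost. They do not remove the conflict. The narrow reading of 5.3.1 still leaves a non-serious polyp in the filtered item, and footnote ff sits on the AESI row. Section 4.4.1 does not define the study period and feeds no adverse event table. The SAP gives no window that would settle which polyps count.

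**Conclusion.** The point holds as a contradiction between passages. For a polyp found at the post-treatment colonoscopy after day 28, 5.3.1 and footnote ff can be read as requiring a belief that the drug caused it, while 5.4 does not. On a 3-month window of 84 to 92 days, 67% to 70% of calendar days lie in the conflict (62 of 90, or 69%, at 90 days).

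Two further inferences should be resisted. The 69% is not a proportion of colonoscopies or of polyps missed. Differential reporting by arm is a possibility that follows from imperfect masking, not something the documents show. The conclusion assumes that sites may have read the rules differently; no information on what they did is available.

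The primary endpoint is unaffected. What is at stake is the randomized comparison of a named AESI. This is worth correcting because the correction is small.

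**What to change.** 1. **Protocol 5.3.1 and Appendix 1 footnote ff.** Reconcile both with 5.4 by adding one sentence: gastrointestinal polyps found at the post-treatment colonoscopy are reported as AESIs regardless of causality.
2. **SAP 4.7.2.** Name gastrointestinal polyps among the events of interest, and count all those found up to and including the post-treatment colonoscopy.
3. **Data already collected.** The Protocol Version 10 rationale gives the last dose as 14 September 2016, so the last 3-month window closed in mid-December 2016 and new wording cannot change what sites reported then. Before the final safety summary, have sites check the post-treatment colonoscopy findings already recorded under 4.4.1 against the Adverse Event eCRF, and enter any polyp not reported, whatever its judged cause. The check should cover both arms in the same way.

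The cost is one protocol sentence, one SAP line and one round of site queries. No new examination is needed.

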5.3.2 Eliciting Adverse Event Information

A consistent methodology of non-directive questioning should be adopted for eliciting adverse event information at all patient evaluation timepoints. Examples of non-directive questions include the following:

“How have you felt since your last clinic visit?”

“Have you had any new or changed health problems since you were last here?”

5.3.3 Assessment of Severity of Adverse Events

The adverse event severity grading scale for the NCI CTCAE v4.0 will be used for assessing adverse event severity. Table 3 will be used for assessing severity for adverse events that are not specifically listed in the NCI CTCAE.

Table 3 Adverse Event Severity Grading Scale

Grade	Severity
1	Mild; asymptomatic or mild symptoms; clinical or diagnostic observations only; or intervention not indicated
2	Moderate; minimal, local, or non-invasive intervention indicated; or limiting age-appropriate instrumental activities of daily living ^a
3	Severe or medically significant but not immediately life threatening; hospitalization or prolongation of hospitalization indicated; disabling; or limiting self-care activities of daily living ^{b, c}
4	Life-threatening consequences or urgent intervention indicated ^d
5	Death related to adverse event ^d

NCI CTCAE=National Cancer Institute Common Terminology Criteria for Adverse Events.

Note: Based on the NCI CTCAE v4.0, which can be found at:

http://evs.nci.nih.gov/ftp1/CTCAE/CTCAE_4.03_2010-06-14_QuickReference_8.5x11.pdf

^a Instrumental activities of daily living refer to preparing meals, shopping for groceries or clothes, using the telephone, managing money, etc.

^b Examples of self-care activities of daily living include bathing, dressing and undressing, feeding one’s self, using the toilet, and taking medications, as performed by patients who are not bedridden.

^c If an event is assessed as a “significant medical event,” it must be reported as a serious adverse event (see Section 5.4.2 for reporting instructions), per the definition of serious adverse event in Section 5.2.2.

^d Grade 4 and 5 events must be reported as serious adverse events (see Section 5.4.2 for reporting instructions), per the definition of serious adverse event in Section 5.2.2.

5.3.4 Assessment of Causality of Adverse Events

Investigators should use their knowledge of the patient, the circumstances surrounding the event, and an evaluation of any potential alternative causes to determine whether or not an adverse event is considered to be related to the study drug, indicating “yes” or “no” accordingly. The following guidance should be taken into consideration:

- Temporal relationship of event onset to the initiation of study drug
- Course of the event, considering especially the effects of dose reduction, discontinuation of study drug, or reintroduction of study drug (where applicable)
- Known association of the event with the study drug or with similar treatments
- Known association of the event with the disease under study
- Presence of risk factors in the patient or use of concomitant medications known to increase the occurrence of the event
- Presence of non-treatment-related factors that are known to be associated with the occurrence of the event

For patients receiving combination therapy, causality will be assessed individually for each protocol-mandated therapy.

5.3.5 Procedures for Recording Adverse Events

Investigators should use correct medical terminology/concepts when recording adverse events on the Adverse Event eCRF. Avoid colloquialisms and abbreviations.

Only one adverse event term should be recorded in the event field on the Adverse Event eCRF.

5.3.5.1 Diagnosis versus Signs and Symptoms

A diagnosis (if known) should be recorded on the Adverse Event eCRF rather than individual signs and symptoms (e.g., record only liver failure or hepatitis rather than jaundice, asterixis, and elevated transaminases). However, if a constellation of signs and/or symptoms cannot be medically characterized as a single diagnosis or syndrome at the time of reporting, each individual event should be recorded on the Adverse Event eCRF. If a diagnosis is subsequently established, all previously reported adverse events based on signs and symptoms should be nullified and replaced by one adverse event report based on the single diagnosis with a starting date that corresponds to the starting date of the first symptom of the eventual diagnosis.

